7.8.1.4 AE summaries for disclosure

The following AE data is needed for disclosure on clinicaltrials.gov and EudraCT. This data will be included in section 16.1.9.2:

- Number of patients with non-serious AEs > of 5 %
- Total number of deaths (all causes – entire study period)
- Total number of deaths resulting from drug-related adverse events
- Total number of serious adverse events
- Total number of serious adverse events related to treatment
- Total number of fatal adverse events
- Total number of fatal adverse events related to treatment

7.8.2 Laboratory data

The analyses of laboratory data will be descriptive in nature and will be based on BI standards ([5](#)).

Baseline for safety laboratory parameters will be the last available measurement before the start of randomized study drug.

Laboratory measurements taken up to 7 days after the last administration of randomized study drug will be considered as on-treatment.

Only patients with at least one available on-treatment value will be included in the analysis of an individual laboratory parameter. All individual data will be presented in listings.

Study visits will be presented by the Visit labels in [Table 6.7.1](#),

7.8.3 Vital signs

Only descriptive statistics are planned for this section of the report.

Proprietary confidential information © 2017 Boehringer Ingelheim International GmbH or one or more of its affiliated companies

7.8.4 ECG

12-lead ECG measurements will be assessed as described in the CTP Flow Chart. ECG-findings before first intake of study drug will be considered as baseline condition. Any clinically significant new findings in the ECG measurement after the first ECG will be considered as AEs and analyzed as planned in [section 7.8.1](#).

7.8.5 Others

7.8.5.1 C-SSRS

The individual items and categories of suicidal ideation and behaviour from the C-SSRS will be summarized through descriptive statistics according to [section 9.2](#) and [9].

9 ADDITIONAL SECTIONS

9.1 CALCULATION OF NTB TOTAL SCORE

Below is a description for the NTB along with detail on deriving the scores for the total scores and several subscales. The derivations are based on [6] and the supplementary information from [7].

Table 9.1: 1 NTB description and scoring

The NTB is a cognitive assessment made up of the following 9 component tests:

1. Wechsler Memory Scale Visual Paired Associates—Immediate (WMVis-I), range 0 to 18;
2. Wechsler Memory Scale Verbal Paired Associates—Immediate (WMVer-I), range 0 to 24;
3. Rey Auditory Verbal Learning Test—Immediate (RAVL-I), range 0 to 105;
4. Wechsler Memory Scale—Digit Span (WMDS), range 0 to 24;
5. Controlled Word Association Test (COWAT);
6. Category Fluency Test (CFT);
7. Wechsler Memory Scale Visual Paired Associates—Delayed (WMVis-D), range 0 to 6;
8. Wechsler Memory Scale Verbal Paired Associates—Delayed (WMVer-D), range 0 to 8;
9. Rey Auditory Verbal Learning Test—Delayed (RAVL-D), range 0 to 30.

The first 3 tests assess immediate memory (WMVis-I, WMVer-I, RAVL-I), the second 3 assess executive function (WMDS, COWAT, CFT), and the last 3 assess delayed memory (WMVis-D, WMVer-D, RAVL-D). Higher scores indicate better cognition on all tests.

First, a total score for each component test except the RAVL-D is calculated by summing all the scores. For the RAVL-D, the total score is calculated as:

total part 7 + total part 8 correct + (15 - total part 8 incorrect).

Then, a z-score for each component test is calculated as follows. For each subject j , at assessment time point t (with $t = 0$ denoting baseline), let y_{ijt} denote subject j 's score at time t for the i th component test ($i = 1, \dots, 9$). Then the corresponding z-score, denoted z_{ijt} , is defined as:

$$z_{ijt} = (y_{ijt} - \bar{y}_{ij\theta}) / s_{ij\theta}$$

Proprietary confidential information © 2017 Boehringer Ingelheim International GmbH or one or more of its affiliated companies

Where y_{i0} and s_{i0} denote the average and the standard deviation of the baseline scores on the i th component test across all study subjects in the FAS.

Finally, the NTB total score z_{jt} for the j th subject at time t is calculated by averaging the 9 component test z-scores:

$$z_{ijt} = (z_{1jt} + \dots + z_{9jt})/9$$

The NTB total z-score will be calculated only if scores for at least 6 of the 9 component tests are not missing [6].

In addition, the following subscales are defined:

- NTB Immediate Memory z-score - average of the 3 immediate memory component test z-scores;
- NTB Delayed Memory z-score - average of the 3 delayed memory component test z-scores;
- NTB All Memory z-score - average of all 6 memory component test z-scores;
- NTB Executive Function z-score - average of the 3 executive function component test z-scores.
-

The Immediate Memory, Delayed Memory, and Executive Function z-scores will be calculated only if at least 2 of the 3 components tests are not missing. The All Memory z-score will be calculated only if at least 4 of the 6 components tests are not missing.

The NTB total z-score (as well as NTB Immediate Memory, NTB Delayed Memory, NTB All Memory, and NTB Executive Function z-scores) will be analyzed using the same MMRM as described for the primary analyses. These analyses will be conducted for the FAS.

Proprietary confidential information © 2017 Boehringer Ingelheim International GmbH or one or more of its affiliated companies

9.2 C-SSRS FDA CATEGORIES

Eleven FDA categories and equivalent C-SSRS categories as the standard for classifying suicidal ideation and behavior

Table 9.2.1 CSSRS and FDA categories

FDA Categories	Equivalent C-SSRS categories

Suicidal ideation:
 
 1. Passive 2. Active: Nonspecific (no method, intent, or plan) 3. Active: Method, but no intent or plan 4. Active: Method and intent, but no plan 5. Active: Method, intent, and plan 
Suicidal behavior:
 
 6. Preparatory actions toward imminent suicidal behaviors 7. Aborted attempt 8. Interrupted attempt 9. Suicide attempt 10. Completed suicide 11. Self-injurious behavior, no suicidal intent 	
Suicidal ideation:
 
 1. Wish to be dead 2. Non-specific active suicidal thoughts 3. Active suicidal ideation with any methods (not plan) without intent to act 4. Active suicidal ideation with some intent to act, without specific plan 5. Active suicidal ideation with specific plan and intent 
Suicidal behavior:
 
 6. Preparatory acts or behaviour 7. Aborted attempt 8. Interrupted attempt 9. Non-fatal suicide attempt 10. Completed suicide 11. Self-injurious behavior without suicidal intent

9.3 SAS CODE

The below table summarizes the SAS code for the main analyses

Table 9.3.1 SAS Code for main analyses

Analysis	Code	Comments
Dose response	
Test the following model:
 $\mu(d_i) = \beta_0 + \beta_1 d_i + \beta_2 d_i^2$ 
PROC GLM DATA=one;
 
MODEL chgept = trt trt*trt;
 
RUN;
 
Treat BID dose as an in between dose = (QD + 2*QD)/2
	
Dose is treated as a continuous variable.
 
$\mu(d_i)$ denotes the mean response of dose level i.

MMRM	
PROC MIXED DATA=dat cl method=reml ORDER=formatted;
 
CLASS trt visit patient ;
 
MODEL chgept = trt baseline visit trt*visit baseline
 
/ ddfm=KR solution;
 
REPEATED visit / type=un subject=patient r rcorr ;
 
LSMEANS trt*visit / pdiff=all cl;
 
RUN ;
	
ANCOVA	
PROC MIXED data=one METHOD=reml ORDER=formatted;
 
CLASS trt ;
 
MODEL chgept = baseline trt ;
 
LSMEANS trt / CL DIFF OM ;
 
RUN;
	

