### 7.2 NULL AND ALTERNATIVE HYPOTHESES

The objective of this exploratory trial is to demonstrate proof-of-concept and also explore the dose response of BI 409306 in NTB total score change from baseline (Visit 3) after 12 weeks treatment. The hypotheses testing will be carried in the following steps. No multiplicity adjustment will be made; hence all the p-values will be descriptive. All tests will be tested at a two-sided alpha 0.05.

- Step 1 for Proof-of-Concept:

$H_{1-0}$ : Mean NTB response of pooled doses of 10 mg QD, 25 mg QD, 25 mg BID and 50 mg QD = Mean NTB response of placebo

$H_{1-a}$  : Mean NTB response for pooled doses of 10 mg QD, 25 mg QD, 25 mg BID and 50 mg QD  $\neq$  Mean NTB response of placebo

If the null hypothesis  $H_{1-0}$  is rejected in favour of  $H_{1-a}$ , then the proof of concept is established.

- Step 2 for dose response finding:

A regression model will be fitted first as the following functional form.

$$\mu(d_i) = \beta_0 + \beta_1 d_i + \beta_2 d_i^2,$$

where  $\mu(d_i)$  denotes the mean response of NTB of the dose level  $i$  group,  $d_i$  denotes for dose levels  $i$ , for  $i = 1, 2, \dots, 5$  and  $\beta$ 's are the coefficients. The dose  $d_i$  will be treated as continuous variable.

Testing for linear dose response curve

$$H_{2-0}: \beta_1 = 0, \beta_2 = 0$$

$$H_{2-a}: \beta_1 \neq 0, \beta_2 = 0$$

If the null hypothesis  $H_{2-0}$  is rejected in favour of  $H_{2-a}$ , then the following test will be tested for quadratic dose response curve.

$$H_{3-0}: \beta_2 = 0$$

$$H_{3-a}: \beta_2 \neq 0$$

- Step 3:

Once the dose response curve is determined from Step 2, the dose group with peak response in the selected model will be tested as follows:

$H_{4-0}$ : The dose group with peak response in the respective model Mean NTB response = Mean NTB response of placebo.

$H_{4-a}$ : The dose group with peak response in the respective model Mean NTB response  $\neq$  Mean NTB response of placebo.

In addition to the 3 steps above, the confidence intervals of difference in treatment effect against placebo will be presented for efficacy evaluation.

Note Step 1 and Step 3 the testing will be based on the adjusted means of NTB response from the primary model as described in [section 7.3](#)

For the secondary endpoint, all calculated p-values should be considered as descriptive for the analysis of secondary endpoint. Therefore, no alpha correction will be carried out.

Proprietary confidential information.

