#### 7.4 HANDLING OF MISSING DATA

Every effort will be made to collect complete data at the specified time points.

In general, completely missing visits will be handled through the statistical model.

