#### 7.5 RANDOMIZATION

Eligible patients will be randomly assigned to one of the 5 treatment groups, with an allocation of 2:1:1:1:1 respectively for placebo: BI 409306 10 mg once daily: BI 409306 25 mg once daily: BI 409306 50 mg once daily once daily: BI 409306 25 mg twice daily.

The randomization will not be stratified.

The randomization of patients to the treatment groups will be performed via an interactive response technology (IRT). BI will arrange for the randomization as well as packaging and labeling of study medication. The randomization list will be generated using a validated system, which involves a pseudo-random number generator and a supplied seed number so that the resulting allocation of medication numbers to treatment is both reproducible and non-predictable. The access to the randomization codes will be controlled and documented.

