#### 7.6 DETERMINATION OF SAMPLE SIZE

The primary efficacy hypothesis will be tested by comparing the dose group of BI 409306 with the peak response in the fitted regression model to the placebo group on the primary

Proprietary confidential information.

© 2017 Boehringer Ingelheim International GmbH or one or more of its affiliated companies. All rights reserved.

This document may not - in full or in part - be passed on, reproduced, published or otherwise used without prior written permission.

endpoint, the change from baseline in NTB total score after 12-week treatment. (See [section 7.2](#) for the details of hypothesis testing.)

As previously mentioned, the randomization allocation ratio of 1:1:1:1:2 of 10 mg, 25 mg, 50 mg, 25 mg BID of BI 409306, and placebo is used so that 33 % of patients will be randomized to placebo. Since these results in an unequal allocation of treatment to placebo, the sample size required for the active treatment and placebo for various effect size are displayed separately. The sample size calculations in [Table 7.6:1](#) displays the range of effect sizes considered for this trial under these assumptions using a 2-sided alpha of 0.05 with 80 % power. The two-sample t-test method with unequal n's in nQuery Advisor 6.01 was used for the calculation.

Table 7.6: 1 Sample size calculations

Standardized effect size	0.45	0.50	0.55	0.6	0.65
Power	80%	80%	80%	80%	80%
n for each active treatment arm	59	48	40	34	29
n for placebo arm	118	96	80	68	58
Total	354	288	240	204	174

Based on the calculations provided in [Table 7.6:1](#), a sample size of 48 per active treatment arm and 96 for placebo arm was selected as adequate for a phase II proof of concept trial. This sample size would allow us to detect an effect size of 0.5 with 80 % power or an effect size of 0.6 with 92 % power, 2-sided alpha at 0.05.

*Assuming a 10% dropout rate, this sample size would allow us to detect an effect size of 0.53 with 80% power and assuming a 20% dropout rate, this sample size would allow us to detect an effect size of 0.56 with 80% power, 2-sided alpha at 0.05.*

Proprietary confidential information.

© 2017 Boehringer Ingelheim International GmbH or one or more of its affiliated companies. All rights reserved.  
This document may not - in full or in part - be passed on, reproduced, published or otherwise used without prior written permission.

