6.6.1 Missing efficacy data

NTB

Details on scoring with missing items are described in [section 9.1](#).

ADAS-Cog11

If a patient has 3 or fewer missing ADAS-Cog/11 items, the following algorithm will be used to compute the ADAS-Cog/11 total score:

Total score = [(total score from completed items) / (maximum total score for completed items)]*(maximum total score[=70] for all items in the scale)

Proprietary confidential information © 2017 Boehringer Ingelheim International GmbH or one or more of its affiliated companies

If there are more than 3 missing ADAS-Cog/11 items, ADAS-Cog/11 score will be considered missing at that time point.

ADCS-ADL-MCI

For ADCS-ADL-MCI, if <30% of the items are missing, the total score will be imputed. The sum of the nonmissing items will be prorated to the sum of total items. The imputed number will be rounded up to the nearest integer. If the nearest integer is greater than the maximum possible score, the imputed score will be equal to the maximum score. If >30% of the items are missing, the total score at that visit will be considered missing. For e.g Total score = [(total score from completed items) / (maximum total score for completed items)]*(maximum total score[=69] for all items in the scale)

Supplementary material for [\[8\]](#).

CDR-SB

If only 1 box (of 6) of the CDR is missing, the sum of the boxes will be imputed by prorating the sum from the other 5 boxes. If the score from more than 1 box is not available, the CDR-SB at that visit will be considered missing. For e.g Total score = [(total score from completed items) / (maximum total score for completed items)]*(maximum total score[=18] for all items in the scale) Supplementary material for [\[16\]](#).

Observed cases (OC) analysis

For all efficacy endpoints using MMRM analyses, it is planned to analyze only the available data that were observed while patients were on treatment, i.e., excluding the missing data. In other words, OC analysis will be performed and missing data in this analysis will not be replaced.

The following imputation methods will be used if the rate of missing data is greater than 5%.

The method below will be used for the endpoints using ANCOVA analyses.

Last observation carried forward (LOCF) analysis

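### Step 2 is coded outside the MMRM with an undefined input; on the natural reading, patients whose only post-baseline NTB is in the Week 4 window inform Steps 1 and 3 but not Step 2

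*SAP*

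**What the plan says.** Protocol 7.2 sets out three steps for the NTB total z-score. The model for two of them is explicit: "Note Step 1 and Step 3 the testing will be based on the adjusted means of NTB response from the primary model". Step 2 is a separate regression of the mean response on dose and dose squared, and the group at the peak of the selected curve goes to Step 3. "All tests will be tested at a two-sided alpha 0.05", without multiplicity adjustment, and the p-values are called descriptive.

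SAP Table 9.3.1 codes Step 2 as PROC GLM on a data set called `one`, with "MODEL chgept = trt trt*trt". There is no visit, patient or REPEATED term. The MMRM row of the same table uses a data set called `dat`, with visit as a repeated factor and unstructured covariance.

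On missing data, protocol 7.4 says "In general, completely missing visits will be handled through the statistical model" and refers to the repeated-measures model of 7.3.1. SAP 6.6.1 prescribes observed cases for MMRM endpoints. For LOCF it says "The method below will be used for the endpoints using ANCOVA analyses"; SAP 7.5.2 names those endpoints as ADAS-Cog11 and ADCS-ADL-MCI. SAP 9.1 places the NTB total score under the MMRM.

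**The concern.** A likelihood-based repeated-measures model uses the Week 4 NTB of a patient who has no Week 12 value. A one-record regression of Week 12 change cannot, because PROC GLM deletes a record whose outcome is missing. So the step that describes the dose response and points to the group for Step 3 can rest on fewer patients, and on a stronger missing-data assumption, than the two steps around it.

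Under the missing-at-random assumption of protocol 7.4, leaving may depend on the observed Week 4 score. The MMRM accommodates that; a complete-case regression without the Week 4 score does not. If such leaving also differs by dose, the remaining Week 12 means shift by dose, and Step 2 can show or hide a trend that the primary model does not support.

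**Working it through.** **The plan's own figures.** Inputs: 48 per active arm and 96 on placebo (protocol 7.6), allocation 2:1:1:1:1 (7.5), two-sided alpha 0.05 (7.2). For an effect of 0.5 the noncentrality is 0.5 × √(48 × 96/144) = 0.5 × √32 = 2.83; the exact noncentral t gives 80.2% power. With dropout the detectable effect is 0.5/√0.9 = 0.527 and 0.5/√0.8 = 0.559, matching the stated 0.53 and 0.56. The sample-size section is sound; its dropout rates serve only as inputs here.

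**Who is in which analysis** (FAS rule in protocol 7.3 and SAP 6.3; windows in SAP Table 6.7:2; Step 2 read as one Week 12 record per patient):

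| Post-baseline on-treatment NTB | MMRM (Steps 1, 3) | GLM (Step 2) |
|---|---|---|
| None | no | no |
| Days 2 to 57 only (Week 4 window) | yes | no |
| Any from Day 58 (Week 12 window) | yes | yes |

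Only the middle row is affected. It includes an early EOT visit up to Day 57, which the SAP assigns to Week 4. Total dropout is 288 × 0.10 ≈ 29 or 288 × 0.20 ≈ 58; these are upper limits on the middle row.

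**Dropout unrelated to response.** Assume SD 1, a true slope of 0.5 SD over 0 to 50 mg and a Week 4 to Week 12 correlation of 0.6 (none of these is in the documents). The SAP codes the BID arm as (25 + 50)/2 = 37.5.

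- Mean dose = 48 × (10 + 25 + 37.5 + 50)/288 = 20.42.
- Sum of squares about the mean = 48 × (100 + 625 + 1406.25 + 2500) − 288 × 20.4167² = 222,300 − 120,050 = 102,250.
- SE of the 0-to-50 mg slope with full data = 50/√102,250 = 0.1564.
- With a fraction p missing, the variance is multiplied by 1/(1 − p) for complete cases and by about ρ² + (1 − ρ²)/(1 − p) for the likelihood model. Power ≈ Φ(0.5/SE − 1.96).

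| p | SE, GLM | SE, likelihood | Power, GLM | Power, likelihood |
|---|---|---|---|---|
| 10% | 0.1648 | 0.1618 | 86% | 87% |
| 20% | 0.1748 | 0.1684 | 82% | 84% |

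Simulation gives 85% against 86% and 81% against 84%. The loss is about 1 and 3 points.

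**Dropout that depends on Week 4 change and differs by dose.** Simulation with 4,000 trials per scenario, planned arm sizes, the assumptions above and a true slope of zero. Poorer Week 4 responders are more likely to leave, and every dropout is taken to be in the affected row:

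| Dropout, 0 to 50 mg | Log-odds per SD | GLM slope bias | GLM type I error |
|---|---|---|---|
| 10% to 20% | 1 | +0.05 SD (about 0.3 SE) | 6% |
| 5% to 25% | 1 | +0.10 SD (about 0.6 SE) | 8 to 9% |
| 5% to 25% | 2 | +0.14 SD | 13% |

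The likelihood slope is unbiased, with about 5% error throughout. In the second row, correlations of 0.4 and 0.8 give biases of 0.07 and 0.13 SD. If dropout instead falls from 25% on placebo to 5% at 50 mg, with a true slope of 0.5 SD, GLM power is 66 to 67% against 84%.

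If only about two-thirds of dropouts are in the affected row (uniform leaving times over 12 weeks, an assumption), the three biases fall to about 0.04, 0.06 to 0.07 and 0.10 SD, with type I error of about 5%, 6% and 9%. These move by about 0.01 SD with how the affected patients are drawn. If response-dependent dropout is equal across arms, there is no slope bias and error stays near 5%.

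**Effect on the selected group.** A separate simulation ran the linear-then-quadratic procedure on a flat-topped curve (true means 0, 0.25, 0.5, 0.5 and 0.4 SD for placebo, 10 mg, 25 mg, 25 mg BID and 50 mg). Dropout was 10/10/15/20/30% in that order, with low Week 4 responders four times as likely to leave, and correlations of 0.5 to 0.7. Complete cases pointed to 50 mg in 57 to 60% of trials, against 42 to 43% with full data.

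**The case against.** The strongest objection is that `one` is undefined, and the ANCOVA row of the same table reads from a data set of that name, to which LOCF and BOCF can apply. If `one` is LOCF-filled, no FAS patient is lost. The SAP contents also show blacked-out entries after 7.4.1 and between 6.3 and 6.5, and the abbreviations list MCPMod and multiple imputation, which the visible text never uses, so a rule may exist out of sight. This stands: a reader might infer that Step 2 drops every patient without a Week 12 NTB, but the documents do not say so. It does not dispose of the point. LOCF has no visible assignment to NTB and would still differ from the MMRM. A data set with both visits would treat two records from one patient as independent and mix Week 4 with Week 12.

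Second, harmful bias needs dropout that is both response-dependent and dose-graded. The protocol gives some reason to expect dose-related leaving: section 1.2 describes concentration-related pulse and visual effects, and 3.3.4.1 has a pulse-based withdrawal rule at Visit 3. Nothing in it shows that leaving depends on Week 4 NTB. That part remains an assumption.

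Third, a rising linear fit peaks at 50 mg whoever is included, so the selected group changes only through a flip in significance or through the quadratic stage. That is correct and limits the consequence.

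Finally, the trial is exploratory, the p-values are descriptive, Step 3 uses MMRM means, and confidence intervals against placebo are presented alongside. A distorted Step 2 could be noticed. This lowers the stakes without justifying the mismatch.

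**Conclusion.** The point holds in a limited form. As coded, Step 2 does not use the model of Steps 1 and 3, and the visible text gives neither its input data set nor a missing-data rule for it. On the natural reading, FAS patients whose only NTB after baseline is in the Week 4 window are left out of Step 2 alone: at most about 29 patients at 10% dropout and 58 at 20%.

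At a correlation of 0.6, the cost with unrelated dropout is small (1 to 3 points of power). With dropout that is both response-dependent and dose-graded, the slope bias is roughly 0.04 to 0.14 SD and type I error runs from about nominal to 13%; this is conditional on assumptions the documents do not supply. A reader might go further and conclude that Step 2 will select the wrong group. The documents do not support that: it would need such dropout together with a curve whose peak is not clear-cut. This is a change worth making before unblinding, not a fault in the primary comparison.

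**What to change.** In SAP Table 9.3.1 and protocol 7.2 Step 2, replace the PROC GLM with the primary repeated-measures model. Substitute continuous dose and dose squared, each crossed with visit, for the treatment factor. Keep baseline and baseline-by-visit as in protocol 7.3.1, with REML and unstructured covariance on all FAS records from Weeks 4 and 12, and test the Week 12 dose terms. A near-equivalent is to regress the five Week 12 MMRM adjusted means on dose by generalised least squares, using their estimated covariance matrix. Name the input data set and state that all three steps use the same patients and missing-data model.

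The cost is SAP wording and a few lines of SAS, with no new data or patients. The drawback is small: Step 2 then rests on the same missing-at-random and covariance assumptions as the primary analysis, and its intervals may be slightly wider than complete-case ones when dropout is selective.

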Name of finished product: NA				
Name of active ingredient: BI 409306				
Protocol date: 27 June 2014	Trial number: 1289.5		Revision date: 17 Feb 2017	
mode of admin.: Tablet, Oral				
Comparator products: Placebo to match BI 409306				
dose: NA				
mode of admin.: Tablet, Oral				
Duration of treatment: 12 weeks				
Criteria for efficacy: Primary endpoint: 

- Change in cognition as measured by change from baseline in Neuropsychological Test Battery (NTB) total score after 12-week treatment.

 Secondary endpoints include: 

- Change from baseline in ADCS-MCI-ADL total score after 12-week treatment

- Change from baseline in CDR-SB total score after 12-week treatment

- Change from baseline in ADAS-cog11 (Alzheimer's Disease Assessment Scale-cognitive subscale) total score after 12-week treatment

				
Criteria for safety: Adverse events, vital signs, 12-lead electrocardiograms (ECG) and routine laboratory tests, Columbia-Suicide Severity Rating Scale (C-SSRS).				
Statistical methods: Restricted Maximum Likelihood Estimation based Mixed-effects Model for Repeated Measures (MMRM) will be used to obtain adjusted means for the treatment effects. This model will include fixed, categorical effects of treatment, visit and treatment by visit interaction, as well as continuous fixed covariates of baseline and baseline-by-visit interaction. Patient will be considered as random effect. The unstructured covariance structure will be used as covariance structure for within-patient variation				
Descriptive statistics				

Proprietary confidential information.

© 2017 Boehringer Ingelheim International GmbH or one or more of its affiliated companies. All rights reserved.

This document may not - in full or in part - be passed on, reproduced, published or otherwise used without prior written permission.

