#### Primary analysis model

The restricted maximum likelihood (REML) based mixed effects model with repeated measurements (MMRM) will be used for the change from baseline in NTB total score after 12 weeks of treatment. The model will include fixed, categorical effects of treatment, visit and treatment by visit interaction, as well as the continuous fixed covariates of baseline and baseline-by-visit interaction. Patient will be considered as random effect. The unstructured covariance structure will be used to model the within patient errors. If this analysis fails to converge, compound symmetry covariance structure might be used. The Kenward-Roger approximation will be used to estimate denominator degrees of freedom. Analyses will be implemented using SAS PROC MIXED. The primary treatment comparisons will be the contrast between treatments after 12 weeks of treatment. Adjusted mean values as well as treatment contrasts will be presented together with the 95 % confidence intervals.

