4 CHANGE IN THE PLANNED ANALYSIS OF THE STUDY

The following changes were made:

The data for patients entered prior to Amendment 3 will be handled as follows:

- The data for assessments removed from the study completely or for a specific visit due to the amendment will be summarized descriptively.

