7.4.1 Primary efficacy analysis

The primary analysis and hypothesis testing are described in section 7.3.1 of the CTP.

Proprietary confidential information © 2017 Boehringer Ingelheim International GmbH or one or more of its affiliated companies

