7.5.2 Other Secondary endpoints

The same primary analysis model will be performed for the secondary endpoint CDR-SB.

The secondary endpoints ADAS-Cog11 and ADCS-ADL-MCI will use the following model:

ANCOVA:

Analysis of covariance will be used for the change from baseline secondary endpoint score after 12 weeks of treatment; terms include baseline value for secondary endpoint measure and treatment.

[REDACTED]

[REDACTED]

[REDACTED]

[REDACTED]

Proprietary confidential information © 2017 Boehringer Ingelheim International GmbH or one or more of its affiliated companies

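### The SAP's MMRM code lists baseline twice and omits the protocol's baseline-by-visit term, and the Step 2 dose-response regression leaves baseline NTB out altogether

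*SAP*

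**What the plan says.** **Primary MMRM.** Protocol 7.3.1 lists treatment, visit and their interaction, "as well as the continuous fixed covariates of baseline and baseline-by-visit interaction". The synopsis says the same: "as well as continuous fixed covariates of baseline and baseline-by-visit interaction". SAP 7.4.1 adds no model of its own: "The primary analysis and hypothesis testing are described in section 7.3.1 of the CTP". SAP section 4, where changes to the planned analysis are declared, deals only with assessments dropped by a protocol amendment ("The data for patients entered prior to Amendment 3 will be handled as follows") and lists no change of model. The code in SAP Table 9.3.1 is "MODEL chgept = trt baseline visit trt*visit baseline".

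The primary model is reused elsewhere. SAP 7.5.2 says "The same primary analysis model will be performed for the secondary endpoint CDR-SB". SAP 9.1 says that the NTB total and four NTB subscale z-scores "will be analyzed using the same MMRM as described for the primary analyses". That makes six endpoints: NTB total, CDR-SB and the four subscales.

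**Step 2.** Protocol 7.2 models the mean NTB response as an intercept plus dose plus dose squared. The PROC GLM code in SAP Table 9.3.1 follows this exactly, with no baseline term. Protocol 7.2 bases Steps 1 and 3 on the adjusted means of the primary MMRM. The ANCOVA for ADAS-Cog11 and ADCS-MCI-ADL also adjusts: "terms include baseline value for secondary endpoint measure and treatment". Step 2 is the only one of the three models in Table 9.3.1 without baseline. It determines the dose with the peak response. Step 3 then tests that dose against placebo, and protocol 7.6 presents this comparison as the primary efficacy hypothesis.

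**The concern.** The first issue is fidelity to the pre-specified model. Listing a covariate twice in a MODEL statement has no effect, so the printed code fits a common baseline slope at both post-baseline visits where the protocol allows one slope per visit. A programmer who copies the table would run a primary analysis that differs from the protocol's and could repeat it for the other five endpoints.

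The second issue is efficiency and coherence. Baseline NTB is collected in every patient and used in Steps 1 and 3, yet Step 2 ignores it without a stated reason. The dose is chosen under one adjustment and tested under another. Some precision is given up at the point that decides whether a dose response is declared and which dose goes forward.

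**Working it through.** **The plan's own figure.** A two-sample t-test with 48 v 96 patients and effect 0.5 has non-centrality 0.5 × √(48×96/144) = 0.5 × √32 = 2.83 on 142 df, which gives 80.2% power. At effect 0.6 the power is 92.1%. Both agree with protocol 7.6. Neither uses baseline, so neither changes below.

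The documents give no NTB variances, baseline slopes or correlations. Those used below are assumptions, shown as ranges.

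**(a) Common slope in place of visit-specific slopes.** Let *b* hold the true slopes of change on baseline at Weeks 4 and 12, R the residual covariance, β the fitted common slope, and baseline variance 1. The misfit goes into the covariance: S = R + (*b* − β)(*b* − β)ᵀ. The Week 12 SE ratio is √(S₂₂/R₂₂). With equal residual variances β is the midpoint, so the ratio is √(1 + δ²/R₂₂), with δ half the slope difference. R₂₂ runs from 0.64 to 0.3:

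| Slopes, Week 4 / Week 12 | δ | SE ratio | Power, 48 v 96, effect 0.5 |
|---|---|---|---|
| equal | 0 | 1.000 | 80.2% |
| −0.2 / −0.3 | 0.05 | 1.002–1.004 | 80.1–79.9% |
| −0.15 / −0.35 | 0.10 | 1.008–1.017 | 79.6–78.9% |
| −0.1 / −0.4 | 0.15 | 1.017–1.037 | 78.8–77.3% |

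A REML simulation with 10 to 20% missing at Week 12 (150 runs per scenario) gave ratios of 1.00 with equal correlations at both visits and 1.015 to 1.052 where the baseline correlation fell between visits. The 1.052 came from correlations of 0.9 and 0.6. These imply slopes of −0.1 and −0.4 again, but with unequal residual variances (1 − 0.9² = 0.19 and 1 − 0.6² = 0.64).

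**(b) Step 2 with and without baseline.** With equal variances s² and correlation ρ between baseline and Week 12, the variance of change is 2(1 − ρ)s² and the residual variance after adjustment is (1 − ρ²)s². Their ratio, adjusted over unadjusted, is (1 + ρ)/2:

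- ρ = 0.9, 0.8, 0.7, 0.6 gives 0.95, 0.90, 0.85, 0.80.
- The SE falls by 2.5% (√0.95 = 0.975) to 10.6% (√0.80 = 0.894).
- This equals 5% (1/0.95) to 25% (1/0.80) more patients.

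Power of the linear test uses n = 96, 48, 48, 48, 48 at doses 0, 10, 25, 37.5, 50, with BID scored as in SAP Table 9.3.1. The mean dose is 48 × 122.5/288 = 20.42 and Sxx = 102,250. The SD of change is 1.

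- *Linear curve reaching 0.5 SD at 50 mg.* The slope is 0.01, so the non-centrality is 0.01 × √102,250 = 3.20 and power is 89.0%. Dividing by √0.95 to √0.80 gives 3.28 to 3.58 and power of 90.5, 91.9, 93.3 and 94.6%.
- *Umbrella with means 0, 0.25, 0.5, 0.5, 0.25.* The fitted slope is 750/102,250 = 0.00733. Lack of fit adds 6.50/286 = 0.023 to the residual variance. The non-centrality is 0.00733 × 319.8/√1.023 = 2.32 and power is 63.7%. With baseline it is 65.9, 68.2, 70.6 and 73.1%.

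The whole of Step 2 was then simulated: linear test, quadratic test if that passes, highest fitted active dose taken forward. There were 12,000 trials per cell, with Monte Carlo SE at most 0.5 points. Trials that pass the linear test and name a truly best dose:

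| Truth | Without baseline | With baseline, ρ = 0.9 / 0.8 / 0.7 / 0.6 |
|---|---|---|
| Linear | about 87% | 88.2 / 89.6 / 90.8 / 92.3% |
| Umbrella (either tied dose counts) | about 45% | 48.2 / 51.6 / 55.0 / 58.7% |

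For the linear curve the choice is right about 97% of the time once the test is passed, with or without baseline, so the gain there comes from passing. For the umbrella, correct choice given a pass goes from 71% to 73–80%.

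**What the loss is relative to.** Step 2 is less precise than the same regression with baseline. It is not in general less precise than the Step 3 contrast, because it borrows strength across doses. Its fitted dose-v-placebo SE is 0.031–0.156 (linear) or 0.092–0.161 (quadratic), against 0.158–0.172 for the adjusted pairwise contrast, which is √(1/48 + 1/96) = 0.177 times √0.80 to √0.95.

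**The case against.** *On the code.* The governing text is right: SAP 7.4.1 points to protocol 7.3.1, and the reuse for CDR-SB and the subscales refers to the described model, not to the code table. The second baseline also sits at a line end in a table cell, where a trailing *visit could have been lost when the PDF was read. The other interaction on that line is intact, which shows that asterisks survive but not that line ends do. These points limit the matter to a reconciliation of code with text. They do not make the code, as it reads, match the protocol.

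*On Step 2.* Protocol and SAP agree with each other, the regression is valid under randomisation, and protocol 7.2 makes all p-values descriptive. Every dose also gets a baseline-adjusted comparison with placebo whatever Step 2 selects, which limits the harm. Protocol 7.2 does not say what happens to Step 3 if the linear test fails, so the simulation's treatment of those trials as naming no dose is an assumption. All of this stands.

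*On size.* The 5 to 20% range assumes equal variances. With a Week 12 to baseline SD ratio k, the unadjusted-to-adjusted variance ratio is (1 + k² − 2ρk)/(k²(1 − ρ²)). At k = 1.1 the excess is 0.0%, 3.3% and 8.6% for ρ = 0.9, 0.8 and 0.7, and at k = 1.25 with ρ = 0.8 it is zero. At k = 0.9 it is larger: 23%, 27% and 33% for the same three correlations. The gain could therefore be nil, but the price of adjusting is then one degree of freedom out of about 285.

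**Conclusion.** Both parts hold.

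The MMRM code as it reads contradicts the model that the SAP's own text adopts. It is probably a slip. It introduces no bias and costs 0 to 3.7% in the Week 12 SE under the assumed slopes with equal residual variances (about 5% in one unequal-variance scenario). The reason to correct it is fidelity to the pre-specified primary analysis, more than the size of the loss.

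Step 2 without baseline is valid but gives up precision wherever change depends on baseline, and it selects the dose under a different adjustment from the one used to test it. For ρ from 0.9 to 0.6 with equal variances, power of the linear test is lower by about 1.5 to 5.6 points (linear curve) or 2 to 9 points (umbrella) than it need be. The loss vanishes if change is unrelated to baseline. No stated sample size or power figure is affected. Both corrections should be made.

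**What to change.** 1. In SAP Table 9.3.1, write the MMRM model as `MODEL chgept = trt visit trt*visit baseline baseline*visit`.
2. For Step 2, write `MODEL chgept = baseline trt trt*trt`. Alternatively, test linear and quadratic dose contrasts on the Week 12 adjusted means of the primary MMRM. The second option aligns selection and testing fully. The first recovers the precision but remains a Week 12-only model.
3. State the choice in protocol 7.2 and the SAP before unblinding. Because the Step 2 equation is in the protocol, this is a change to the planned analysis and should also be declared in SAP section 4.

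The cost is one term in each of two code lines and one line in protocol 7.2, with the amendment step that a protocol change entails. No new data, visits or patients are needed.
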